### **8.1.3. GA Lesion Growth Rate between Timepoints of Interest**

Upon reviewing the 12-month data of the study for the primary analysis, a different growth rate was observed from Month 6 to Month 12 as compared from Baseline to Month 6 for the active group. To assess the growth rate between any two timepoints of interest (Months 6, 12 and 18), the change in GA lesion from Month 6 to Month 12, Month 12 to Month 18, and Month 6 to Month 18 will be summarized. One-way ANOVA will be used to compare the treatment effect on the GA lesion growth between the given timepoints. The pairwise treatment group comparisons will be done based on the least significant different (LSD) t-test to adjust the multiplicity.

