### 4. ENDPOINTS

#### 4.1. PRIMARY EFFICACY ENDPOINT

The primary endpoint is the annual growth rate of GA area in the study eye as measured by the mean change in square root area of GA lesion from baseline to Month 12 based on the Fundus Autofluorescence Photographs (FAF). Baseline will be taken as the last available non-missing assessment prior to first study drug administration, this should be the screening assessment for the primary endpoint.

A secondary endpoint will investigate the untransformed value collected i.e. mean change in area of GA lesion from baseline to Month 12 based on the FAF.

Upon reviewing the 12-month results, different growth rates in the GA lesion were observed across visit to visit. Therefore, the change in GA lesion from Month 6 to Months 12 and 18, and the change from Month 12 to Month 18 will be evaluated as exploratory endpoints. The analyses will be performed for both square root transformed and untransformed measurements of the GA lesion.

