### 6. GENERAL ASPECTS FOR STATISTICAL ANALYSIS

#### 6.1. GENERAL METHODS

All statistical tests will be 2-sided at the 0.1 level of significance. To understand the clinical significance of the estimated treatment effects and to aid interpretation of the formal hypothesis testing 2-sided 95% CI will also be provided. There will not be any adjustments for multiple comparisons.

For all independent ophthalmic assessments (performed by DARC laboratory), if assessments by only two independent readers are available, then the mean of the 2 readings will be used in the calculation of summary statistics. If assessments by three independent readers are available, then the median of the three readings will be used for the summary calculations.

Continuous variables will be summarized using the number of non-missing observations (n), mean, standard deviation (SD), median, minimum, and maximum. Geometric mean and coefficient of variation (CV) will be included for PK parameters, where appropriate. Categorical variables will be summarized using frequencies and percentages. Unless stated otherwise, for all percentages, the number of subjects in the analysis population for the treatment group will be the denominator.

Unless otherwise specified, the estimated mean and median for a set of values should be printed out to 1 more decimal place than the original values, and standard deviations should be printed out to 2 more decimal places than the original values. The minimum and maximum should report the same number of decimal places as the original values. Percentages will be displayed with 1 decimal place; except percentages will not be presented when the count is zero and 100% will be presented as an integer.

Unless stated otherwise, baseline will be taken as the last available non-missing assessment prior to first study drug administration.

Subjects can discontinue treatment but remain in the study for follow-up. All assessments will be included in summary tables or analyses unless stated otherwise.

For all summary tables, data will be presented by treatment group and by pooled sham and pooled APL-2. For summaries by-visit pooled sham and pooled APL-2 will only be presented for the bi-monthly visits. The treatment group labels for summary tables will be:

- APL-2 Monthly
- APL-2 EOM
- APL-2 Pooled
- Sham Monthly
- Sham EOM
- Sham Pooled

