### **13. CHANGE FROM ANALYSIS PLANNED IN PROTOCOL**

The changes from the analyses specified in the protocol are:

1. The definition of the PP population has been updated to exclude any subject who has violated any inclusion or exclusion criteria and/or deviated from the protocol, in a way that could influence their efficacy assessment. The protocol refers to the PP as all randomized subjects who return for 12 month visit which is simply a completer's analysis which is covered in the sensitivity analyses of the primary endpoint.
2. The primary analysis specified in the protocol does not take account of baseline in the model, however as a precaution baseline has been included in the model. If there is no relationship with baseline then only one degree of freedom is lost by including this term in the model.
3. The protocol specified the use of ANOVA on the data at Month 12 with missing data handled by the LOCF or by a non-precise regression method of imputation when imbalance drop-out rates occur across treatment groups. An MMRM approach, which directly utilizes

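### SAP 8.1.3 tests exploratory interval growth by one-way ANOVA on subjects with both images, where the planned MMRM could give the same contrasts, and credits LSD with a multiplicity adjustment it does not make

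*SAP*

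**What the plan says.** SAP 8.1.3 was added after the 12-month results had been reviewed. It looks at "the change in GA lesion from Month 6 to Month 12, Month 12 to Month 18, and Month 6 to Month 18". The test is stated in one sentence: "One-way ANOVA will be used to compare the treatment effect on the GA lesion growth between the given timepoints". The next sentence reads: "The pairwise treatment group comparisons will be done based on the least significant different (LSD) t-test to adjust the multiplicity". The section names no analysis population, number of groups, covariate or missing-data rule, and it sets no condition on the overall F-test before the pairwise tests.

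SAP 4.1 says these changes "will be evaluated as exploratory endpoints" and adds a second scale: "The analyses will be performed for both square root transformed and untransformed measurements of the GA lesion".

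Other parts of the plan bear on this:

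- SAP 6.1 sets two-sided tests at 0.1 and states: "There will not be any adjustments for multiple comparisons".
- SAP 13, item 3, begins: "The protocol specified the use of ANOVA on the data at Month 12 with missing data handled by the LOCF". It then replaces that approach with an MMRM using all available data, as the primary analysis. Item 2 adds baseline to the model as a precaution.
- SAP 8.1 and protocol 11.2.3.2 allow LSD comparisons only after the overall test is significant at 10%. SAP 8.1.1 and 8.2.1 repeat that condition.
- The opening of SAP 8 repeats the change-from-baseline analyses with data to Month 18.

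**The concern.** Two things look wrong.

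First, the plan moves to an MMRM for the primary endpoint in order to account for missing data, then returns to a method without that protection for the intervals that reach furthest into follow-up. By Month 18 cumulative loss can only be equal or greater. If subjects who leave differ in growth from those who stay, and differ more in one arm, the interval contrast mixes treatment effect with selection.

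Second, LSD pairwise tests are unadjusted t-tests. Any protection comes from a preceding overall test, which 8.1.3 does not mention. A report that repeated the sentence would claim error control that the method does not supply, and would contradict SAP 6.1.

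At stake is how far the CSR addendum can rely on comparisons of growth after Month 6 and after treatment ends. The Month 12 primary analysis is not at stake.

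**Working it through.** **The plan's own figure.** Section 8.1.3 states no power or error rate. The nearest figure is the power table in protocol 11.3.3, also a one-way ANOVA: three groups of 67, alpha 0.10. The noncentrality is λ = n Σ(μᵢ − μ̄)² / σ².

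- Means 0.23, 0.23, 0.33 with σ = 0.20 (the value SAP 13, item 5, says was used): λ = 67 × 0.006667 / 0.04 = 11.17, power 91.4%. By symmetry 0.23, 0.33, 0.33 gives the same.
- Means 0.23, 0.28, 0.33: λ = 67 × 0.005 / 0.04 = 8.375, power 82.6%.

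These match the stated 91%, 91% and 83%, so the three-group setting at alpha 0.10 is a fair basis for the error rates below.

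**Multiplicity.** Three groups of 67 leave 201 − 3 = 198 residual degrees of freedom. Each LSD test rejects when |t| > t(0.95; 198) = 1.653. With equal groups, at least one of three pairs rejects when the studentized range exceeds √2 × 1.653 = 2.337.

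- No gate, three pairs: P(q > 2.337; 3 groups, 198 df) = 0.226. Simulation agrees.
- No gate, only the two active-versus-sham pairs: 0.175.
- Overall F-test gate at 0.10: 0.099.
- Across the three overlapping intervals, assuming a correlation of 0 to 0.6 between the two half-year growths: 0.37-0.44 without the gate, 0.18-0.22 with it. The second scale is not counted.
- If the four randomised arms were compared: 0.348 without the gate, and 0.099 with it when all arms are equal. Protected LSD gives strong control only with three groups, so the number of groups matters.

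**Complete-case bias.** For one arm, with R = 1 if both images exist and g the interval growth,

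E(g | R = 1) − E(g) = Cov(g, R) / P(R = 1).

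The bias in the contrast is the active value minus the sham value. It is zero if drop-out is unrelated to growth, and it cancels if growth distribution, rate and mechanism are the same in both arms.

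From the documents: growth 0.33 mm/year, hence 0.165 mm per half-year; SD 0.20 mm/year; a 30% design effect, hence 0.30 × 0.165 = 0.0495 mm per half-year; overall loss 15-20%. Assumed, because the documents give no value: drop-out by arm, odds of drop-out multiplied by 2.0-2.7 per SD of observed growth, between-interval correlation, and measurement error of 0.03-0.06 mm. There is no true treatment difference. Simulated Month 12-18 bias, active minus sham:

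- Same mechanism in both arms, 15% against 20%: at most about -0.004 mm (0.004 / 0.0495 = 8% of the design effect).
- Active arm only, between-interval correlation 0.3-0.6, 15% against 20-25%: about -0.001 to -0.013 mm (up to 26%).
- Active arm only, one constant slope per subject, same rates: about -0.010 to -0.020 mm (20% to 40%).

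A likelihood estimate that conditions on earlier observed values has bias near zero in all these settings.

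**If drop-out depends on unseen growth.** For Month 6-12, active arm only, 15% against 20%, odds ratio 2.7 and correlation 0.3-0.6, complete-case bias is -0.019 to -0.022 mm and MMRM bias is -0.013 to -0.020 mm. The MMRM reduces the bias but does not remove it.

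**The case against.** **The analysis is exploratory and partly covered.** This stands. SAP 4.1 labels it so, and protocol 11.6 bases the Phase III decision on the one-year analysis. A reader might infer that key claims about onset or loss of effect rest on 8.1.3; the documents make no such claims and report only that growth rates differed. The Section 8.1 model extended to Month 18 also yields LS means whose differences are the interval point estimates. Missing are the explicit contrasts with standard errors and intervals.

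**The bias is hypothetical.** Largely so. No document gives a growth-dependent drop-out mechanism. Protocol 11.5 foresees fewer completers in the active arms, but worries there about carrying early areas forward. The largest figures need selection in the active arm only and a constant slope per subject, which sits badly with a section written because growth differed between visits. The sign follows from that assumed selection. What stands is that the plan has a method valid under a weaker assumption and does not use it here.

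**The gate is implied.** This is plausible: ANOVA is named first, and the same LSD wording is gated elsewhere. On that reading the error per interval is about 10%. The text is still silent, and the conflict with SAP 6.1 remains.

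**Section 13 concerns only the primary analysis.** Correct. It sets no rule for exploratory intervals, so 8.1.3 does not breach it. Omitting baseline also has support in protocol 11.2.3.2, which takes square-root change to be independent of baseline size. That premise does not extend to the untransformed scale, which SAP 4.1 also requires.

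**Conclusion.** The point holds as a matter of method choice and wording. Section 8.1.3 uses a complete-case comparison where a contrast from an already planned model would rest on a weaker missing-data assumption, and it attributes to LSD an adjustment that LSD does not make.

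The possible Month 12-18 bias runs from near 0 to about -0.02 mm under the assumptions listed. The upper end is close to a worst case. A reader might conclude that the ANOVA will favour APL-2; the documents do not support that, because the contrast is biased only if drop-out depends on growth and its rate or mechanism differs by arm. Nor is the MMRM a general cure.

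Familywise error per interval is 22.6% if the gate is truly absent and about 10% if it was intended. A reader might take 22.6% as the rate the sponsor chose; the text is silent, so only the ambiguity and the contradiction with SAP 6.1 are certain. Neither part touches the primary result or the study's power.

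**What to change.** In SAP 8.1.3:

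- Fit the Section 8.1 MMRM to Months 2, 6, 12 and 18 in the MITT population, on both scales. Estimate Month 6-12, 12-18 and 6-18 growth as contrasts of the visit LS means for AM, AEOM and pooled sham. Give the differences between groups with 95% confidence intervals. Keep the one-way ANOVA as supportive if wanted, described as based on subjects with both images.
- Delete the claim that LSD adjusts for multiplicity. State that LSD p-values are given only if the 2-df test of equal growth for that interval is significant at 10%.
- State that error is not controlled across the three intervals or the two scales, and that the intervals were chosen after the 12-month results were seen.
- State that the MMRM contrasts assume missing at random, and tabulate by arm the subjects with and without both images for each interval.

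The cost is a few contrast statements in a model already planned to Month 18, plus one short table. No new data are needed.

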## Statistical Analysis Plan

---

### **8.2. SECONDARY AND EXPLORATORY EFFICACY ENDPOINTS AND ANALYSIS**

#### **8.2.1. Best-Corrected Visual Acuity (BCVA)**

The change from baseline in BCVA score over time to Month 12 will be analysed in the same way as the primary endpoint for the MITT population. The model will include the fixed effects of treatment (3 groups: AM, AEOM and Sham), baseline BCVA score, visit (Day 7, Months 2, 4, 6, 8, 10 and 12), treatment by visit interaction, visit by baseline interaction and treatment by baseline interaction. An unstructured covariance structure will be used to model the within subject error. The Kenward-Rogers approximation will be used to estimate the denominator degrees of freedom. If the treatment by baseline interaction is not significant at the 10% level then this term will be removed from the model. If significant at the 10% level results will be presented both including and excluding this term and the nature of the interaction will be investigated before deciding on an approach for presenting results including the treatment by baseline interaction.

The analysis model table will be presented. The treatment comparisons (AM vs Sham, AEOM vs Sham and AM vs AEOM) at Months 6 and 12 will also be presented with the estimate, standard error and 95% CI. If the treatment effect is significant at the 10% level then the treatment means will be compared using the least significant difference (LSD) method and the p-value presented.

The change from baseline in BCVA score will be summarized by treatment group and visit for the MITT population using the observed data. Summaries will present the descriptive statistics for baseline, absolute values and change from baseline data.

The estimated mean change from baseline in BCVA score  $\pm$  SE of mean change, will be plotted over time by treatment group. The plot will be repeated for the observed mean change from baseline in BCVA score  $\pm$  SE of mean change.

The categorical changes (improvements of  $\geq 5$  to  $<10$ ,  $\geq 10$  to  $<15$  and  $\geq 15$ , minimal/no change, worsening of  $\geq 5$  to  $<10$ ,  $\geq 10$  to  $<15$  and  $\geq 15$ , and missing changes) will be summarized by treatment group and visit for the MITT population.

The Snellen equivalent categorical response will be summarized by treatment group and visit for the MITT population. The observed logMAR changes from baseline will also be summarized by treatment group and visit for the MITT population. The listing of BCVA data will also include the logMAR values.

The relationship between GA lesion size change from baseline as recorded by FAF and changes from baseline in BCVA will also be investigated. A scatter plot of changes from baseline at Month 12 in GA lesion size as measured by FAF versus changes from baseline at Month 12 in BCVA will be presented. Treatment groups will be identified on the plot. The Pearson correlation coefficient for each treatment group will also be presented. Similar summary and figures will be provided for

## Statistical Analysis Plan

---

relationship at Month 18. To assess whether there is a delay in visual acuity decline compared to GA growth, the scatter plot of the changes from baseline for GA lesion at Month 6 vs BCVA at Month 12, and GA lesion at Month 12 vs BCVA at Month 18 will be provided.

### **8.2.2. Macular Neovascularization (MNV)**

The incidence and exposure adjusted incidence of macular neovascularization (MNV) TEAEs in the study eye will be summarized for the MITT population.

Exposure adjusted incidence (or incidence rate per 100-patient-years) = number of subjects experiencing MNV / total subject time at risk (in years) × 100

Total subject time at risk is the time from first study drug administration date to first MNV event date +1 for subjects who experience an event, or time from first study drug administration date to last visit date +1 for subjects who do not experience a MNV event. Total subject time will be presented in years with a year = 360 days for the calculation.

The incidence for the MITT population will be compared between the active treatment groups (APL-2 Monthly or APL-2 EOM) and sham group using a Fisher's exact chi-squared test. The analysis will be repeated by the subgroup fellow eye CNV at baseline.

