4.3 Risk/Benefit

The safety monitoring practices employed by this protocol (e.g. complete ophthalmological exam, IOP monitoring, OCT, vital signs, hematology, serum chemistry, urinalysis, and AE questioning) are adequate to protect the subjects' safety.

There are also risks associated with the ophthalmic procedures required for participants in this study. However, these are all standard procedures that are widely performed in ophthalmology.

In the days following any IVT injection, patients are at risk of developing endophthalmitis. If the eye should become red, sensitive to light, painful, or develop a change in vision, the patient will be instructed to seek immediate care from an ophthalmologist. Other risks of IVT injection include traumatic cataract, retinal detachment and hemorrhage.

Transient increased IOP has also been identified as a risk following IVT injections. IOP will be carefully monitored in this study.

The approximately 150 mL of blood (See [Section 9.9](#)) planned for collection from each subject over the 18 months of the study does not pose an undue risk in this patient population.

Based on data available to date, IVT administration of complement C3 inhibitors does not seem to present an unreasonable ophthalmic or systemic risk to humans. In three previous clinical studies involving 72 subjects undergoing local C3 inhibition with the related compound POT-4/AL-78898A, no drug-related SAEs were reported. Also, a Phase I study with APL-2 in patients with wet AMD has completed and no drug-related SAEs have been reported thus far.

Following a routine scheduled interim review of this ongoing POT-CP121614 (FILLY) study, including data as of April 5, 2017, by the Safety Monitoring Committee, an imbalance in new exudation in subjects treated with APL-2 was observed (further details described in an Investigator Brochure Addendum No. 3, 10 April 2017). Higher rates in new exudation were observed in eyes treated with APL-2, particularly monthly. The risk of developing new exudation may be increased in patients with a prior history of exudative AMD in the fellow eye. Visual acuity in subjects who develop new study eye exudation does not appear to differ significantly from those who do not.

There is a potential health benefit for trial participants from receipt of study drug. We propose to administer APL-2 to patients with GA. If efficacious, APL-2 is expected to alter the course of GA and slow its rate of growth.

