8.3.4 Injection Visits – Monthly or EOM until month 12 -

Monthly Groups: Days 30, 60, 90, 120, 150, 180, 210, 240, 270, 300, 330 and 360 - Visits 4, 5, 6, 7, 8, 9, 10, 11, 12, 13, 14 and 15, respectively.

EOM Groups: Days 60, 120, 180, 240, 300 and 360 – Visits 4, 5, 6, 7, 8 and 9 respectively.

Unless specified, all ophthalmic procedures (including imaging) are to be performed on the **study eye only**. The following procedures will be performed at all injection visits:

1. Obtain information on any changes in medical health and/or the use of concomitant medications.
2. Collect vital signs pre- and post-dose. Vital signs will be measured within approximately 1 hour prior to dosing for the pre-dose time point. Post-dose vital signs readings will be performed within 30 minutes after dosing.
3. Collect blood for PK analysis.
4. Perform urine pregnancy test before APL-2 injection. **-WOCBP only-**
5. Perform BCVA. **-Both eyes on Day 360 only-**
6. Perform LL-BCVA. **-Both eyes on Day 360 only-**
7. Perform a complete ophthalmic exam including slit-lamp exam of the cornea, iris, anterior chamber, lens (LOCS III if any opacity on the lens noted) and aqueous reaction (cells and flare), dilated fundus exam of the vitreous and retina and IOP measurement.
8. Perform the IVT injection of APL-2 (or Sham injection) as described in the MOP.
9. Monitor the study eye within 15 minutes post-injection as outlined in [Section 9.8](#) and in the MOP.
10. Monitor for adverse events.

The following procedures will be performed only at specific visits, as noted:

1. Collect blood and urine for laboratory analysis and forward the samples to the central laboratory. - **Only on Days 60, 180 and 360 for all groups -**
2. Collect blood for genetic marker analysis (if applicable, see [Section 9.3](#)) and forward the samples to the central laboratory. - **Only on Days 60 for all groups -**
3. Perform SD-OCT imaging and forward the images to the CRC. - **Only on Days 60, 180 and 360 for all groups -**
4. Perform FAF imaging **of both eyes** and forward the images to the CRC. - **Only on Days 60, 180 and 360 for all groups -**
5. Perform IR imaging (if applicable) **of both eyes** and forward the images to the CRC. - **Only on Days 60, 180 and 360 for all groups -**

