10.2 Adverse Event Assessment and Recording

The Investigator will probe, via discussion with the subject, for the occurrence of AEs during each subject visit and record the information in the site's source documents. For each AE, the PI should note the start and resolution dates, the severity, whether it meets the definition of an SAE (see [Section 10.1.2](#)), the relationship of the event to the study drug, the action taken regarding study drug, and the outcome of the event. Data should be transcribed from the source documents to the CRF as per the CRF instructions.

When reporting an adverse event, the event description should use the best matching terminology describing the event as found in the "Common Terminology Criteria for Adverse Events" (CTCAE, v 4.03). If an available CTCAE term fits the event well, no additional descriptors may be needed. However, the Investigator should add any necessary descriptions in order to clarify the event or to place it in an appropriate context. If an appropriate term matching the adverse event cannot be found in the CTCAE and you do not know the preferred MedDRA term, the adverse event description should include a diagnosis, sign or symptom with additional information to facilitate subsequent categorization into MedDRA coding terms.

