11.3.2 Treatment allocation

To preserve masking of subjects and assessors, sham injections will be randomly assigned to either a monthly (SM) or every other month (SEOM) arms, but the two sham groups will be pooled for hypothesis testing (S). Thus randomized treatment allocation will be AM: AEOM: SM: SEOM in a 2:2:1:1 fashion. As above, for analysis SM and SEOM will be pooled into a single group, S.

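### MNV incidence in each APL-2 arm is compared with a sham group that mixes two visit schedules, so ascertainment is unequal; schedule-matched sensitivity contrasts would be a cheap, minor improvement

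*SAP*

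**What the plan says.** SAP 8.2.2 plans the incidence and the exposure-adjusted incidence of MNV in the study eye. On testing it says: "The incidence for the MITT population will be compared between the active treatment groups (APL-2 Monthly or APL-2 EOM) and sham group". The method named is Fisher's exact test. SAP 6.1 sets the level and the multiplicity rule: "All statistical tests will be 2-sided at the 0.1 level of significance" and "There will not be any adjustments for multiple comparisons". The MNV sentence does not itself call the sham group pooled. That reading comes from Protocol 11.3.2, which combines SM and SEOM into one group S for hypothesis testing, and from the SAP's models, which carry a single Sham level.

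SAP 4.2.2 identifies MNV cases through a clinical review of ocular adverse events. Under Protocol 10.2 the investigator asks "for the occurrence of AEs during each subject visit". Under Protocol 10.5 disease progression becomes an adverse event only when it requires an intervention.

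Protocol 8.3.4 schedules monthly-arm injection visits every 30 days from Day 30 to Day 360. For the other arms it lists "EOM Groups: Days 60, 120, 180, 240, 300 and 360". BCVA and a dilated fundus examination of the study eye take place at every one of these visits, and also on Day 7 in all arms. SD-OCT and FAF fall on Days 60, 180 and 360 in every arm. Angiography is scheduled only at screening and termination.

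Protocol 4.3 reports an interim safety finding: "Higher rates in new exudation were observed in eyes treated with APL-2, particularly monthly".

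**The concern.** Pooling the two sham arms is harmless for GA area, which is measured on the same days in every arm. MNV is not measured that way: it enters the database through adverse event records, and visits feed those records. AM is set against a control that is half EOM-scheduled, and so examined less often than itself. AEOM is set against a control examined more often than itself.

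The SAP guards against this asymmetry elsewhere. The BCVA model in 8.2.1 uses only visits common to all arms, and 6.1 restricts pooled by-visit summaries to the bi-monthly visits. The MNV comparison has no such rule, although the trial randomises a sham arm for each schedule.

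What is at stake is how the two MNV estimates are read next to each other. New exudation is the safety signal that the protocol itself names, and the schedule mismatch would push the estimates apart in the same direction as that signal.

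**Working it through.** **1. Visit counts.** The inputs are Protocol 8.3.3 and 8.3.4. The documents give no MNV rate, event count or power, so there is no plan figure to reproduce.

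- Monthly arms: Day 7 plus 12 injection visits after Day 0 = 13.
- EOM arms: Day 7 plus 6 = 7.
- Pooled sham, with SM and SEOM equal in size (40 and 40, SAP 3.3): (13 + 7)/2 = 10.
- Relative to the comparator: AM 13/10 = 1.3; AEOM 7/10 = 0.7.

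**2. Direction.** Every EOM visit day is also a monthly visit day. The monthly arms add Days 30, 90, 150, 210, 270 and 330. If the chance of recognising MNV at a given visit is the same in all arms, scheduled visits cannot detect fewer cases on the monthly schedule. The bias is therefore upward for AM and downward for AEOM, or zero.

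**3. Size with no drug effect (assumed model).** Onset is uniform over Days 0 to 360. Signs last D days. Detection probability is *i* on the imaging days (60, 180, 360) and *c* at other visits. For onset at *t*, P(detected) = 1 − Π(1 − s_k) over visits from *t* to *t* + D, averaged over *t*. Call the result d_M for monthly and d_E for EOM. The ratio to pooled sham is d_M/[(d_M + d_E)/2] for AM, and the same with d_E on top for AEOM. The values of *c*, *i* and D are assumptions; dropout, unscheduled visits and spontaneous reports are left out.

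| Signs last | c | i | d_M | d_E | AM/sham | AEOM/sham |
|---|---|---|---|---|---|---|
| persistent | 0.8 | 1.0 | 1.000 | 1.000 | 1.00 | 1.00 |
| persistent | 0.8 | 0.9 | 0.990 | 0.979 | 1.01 | 0.99 |
| persistent | 0.5 | 0.7 | 0.950 | 0.906 | 1.02 | 0.98 |
| persistent | 0.3 | 0.5 | 0.868 | 0.776 | 1.06 | 0.94 |
| 60 days | 0.8 | 0.9 | 0.964 | 0.852 | 1.06 | 0.94 |
| 60 days | 0.5 | 0.7 | 0.789 | 0.603 | 1.13 | 0.87 |
| 30 days | 0.8 | 0.9 | 0.828 | 0.441 | 1.31 | 0.69 |

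Example, fourth row: 0.868/[(0.868 + 0.776)/2] = 0.868/0.822 = 1.06.

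**4. Effect on the planned test.** This is exact enumeration of Fisher's test, two-sided 0.10, 80 versus 40 + 40, with no drug effect. Take a deliberately unfavourable assumption: 90% of cases are recognised under monthly visits and 70% under EOM visits. Pooled sham is then 80%, and the ratios are 0.90/0.80 = 1.13 and 0.70/0.80 = 0.88.

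| True MNV rate | AM vs sham | AEOM vs sham | Complete detection in all arms |
|---|---|---|---|
| 5% | 0.039 | 0.033 | 0.043 |
| 10% | 0.060 | 0.060 | 0.055 |
| 20% | 0.082 | 0.080 | 0.069 |
| 30% | 0.097 | 0.099 | 0.072 |

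In the step 3 model, examined at true rates of 2% to 20%, the nominal 0.10 was exceeded only with 30-day signs (c = 0.8, i = 0.9) at a 20% rate: 0.126 for AM and 0.134 for AEOM.

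**5. Exposure-adjusted rate.** Time at risk ends at the first MNV date. If MNV is found at the next visit, the mean delay is about 30/2 = 15 days on the monthly schedule and 60/2 = 30 days on the EOM schedule. At an assumed 10% incidence the extra time at risk is 0.10 × 15 = 1.5 days per subject, about 0.4% of 360 days. The direction is the same, and the size is negligible next to step 3.

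**6. Cost of matching.** Power of Fisher's test at two-sided 0.10, for assumed sham and APL-2 rates:

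| Rates | Pooled, 80 vs 80 | Matched, 80 vs 40 |
|---|---|---|
| 1% vs 10% | 75% | 54% |
| 2% vs 10% | 60% | 42% |
| 5% vs 20% | 87% | 70% |
| 2% vs 20% | 98% | 93% |

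**The case against.** The strongest reply is that the schedules are more alike than the visit counts suggest. SD-OCT and FAF fall on the same days in all arms, and all arms share the even-month visits and Months 15 and 18. For MNV that persists, the extra monthly visits mainly bring the detection date forward; they seldom decide whether the eye is counted by Month 12. Adverse events can also be reported spontaneously (Protocol 10) or found at unscheduled visits (8.3.7). Because progression must require an intervention to be an adverse event, the count leans towards cases less likely to go unnoticed. All of this stands, and it is why the likely bias is small.

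The reply also holds on display. SAP 6.1 already requires summary tables by treatment group, with SM and SEOM shown separately as well as pooled. A reader might infer that a dosing-frequency effect cannot be told apart from an examination-frequency effect; with all four arms tabulated, that goes too far. It is equally true that 8.2.2 plans no AM versus AEOM test of MNV and that no passage makes this comparison choose a Phase III regimen. Protocol 11.6 ties the Phase III decision only to the one-year analysis in general.

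What the reply does not remove is that the planned test, the only formal comparison of MNV, uses a control matched to neither active arm, while no estimate or interval is planned for the matched contrasts.

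**Conclusion.** The point holds as unequal ascertainment, at minor severity. The counts of 13, 7 and an average of 10 follow directly from the schedule. The direction, upward for AM and downward for AEOM or else zero, needs only equal per-visit detection across arms. The size is not known from the documents. Under the assumed detection rates the ratios to sham are 1.00 to 1.06 for AM and 0.94 to 1.00 for AEOM if MNV persists. They reach 1.13 and 0.87 for 60-day signs, and about 1.31 and 0.69 for 30-day signs.

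Two stronger readings are tempting. One is that the reported monthly exudation signal is an artefact of visit frequency. The documents do not support this: shared imaging and shared visits limit the bias, and nothing in them shows that exudation is short-lived or often missed. The other is that the planned Fisher test is invalid. Its false-positive rate stays below 0.10 in all but the most extreme case tried, so the concern is interpretation of the estimates.

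**What to change.** Keep the pooled-sham Fisher test in SAP 8.2.2. Add, as sensitivity analyses, AM versus SM and AEOM versus SEOM for both incidence and exposure-adjusted rate, reported as estimates with confidence intervals. Optionally add one exact test of APL-2 versus sham stratified by visit schedule (80 versus 40 in each stratum), which keeps all subjects but addresses APL-2 overall, not dosing frequency. State that any reading of dosing-frequency differences in MNV uses the matched contrasts. No new four-arm table is needed.

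The cost is SAP wording and one table from data already collected. Each matched contrast has about 40 sham subjects instead of 80, so its interval is wider; that is why these belong beside the pooled test and should not replace it. Matching removes only the schedule difference. Investigators are unmasked (Protocol 7.2), and any effect of that on which progression is judged to need intervention would remain.
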